5.4.6.5. Pachymetry

Corneal thickness using contact pachymetry will be performed on the central cornea at Screening, Baseline, Week 16, Month 6, Month 9 and Month 12/Exit visits. At each examination, 3 measurements of central corneal thickness (CCT) and associated standard deviation will be reported, and the average of the 3 measurements will be calculated and used for analysis. CCT raw values and their changes from baseline at each post-baseline visit will be summarized descriptively by visit and by treatment cohorts.

5.4.6.6. Biomicroscopy and Dilated Ophthalmoscopy

Biomicroscopic examinations will be performed for each eye at baseline and post-baseline visits. All findings will be coded using MedDRA dictionary.

Number and percentage of participants with findings showing more than one grade increase in severity from baseline or a positive status change, at 1 or more post-baseline visits, will be presented by coded PT in descending order of incidence rate. For findings that are associated with a severity grade, more than 1 severity grade increase in severity from baseline is defined as a change from no finding to 2 and above, from 0.5 to 2 and above, or from 1 to 3 and above from baseline at any of the follow-up visits. Number and percentage of participants with findings that not associated with a severity grade, a positive status change is defined as a finding present at post-baseline which did not present at baseline will be summarized.

Change from baseline in severity grade for gradable findings and status change from baseline for non-gradable findings will be derived at each post-baseline visits. The method to compare with baseline will be by eye, eye area, finding and MedDRA PT. When conducting comparison from baseline, “Other” is consider as a specific finding itself that is different from findings under any pre-defined terms. If the same PT appears under a pre-defined finding and “Other” within the same eye and eye area, they will be compared with baseline separately.

Dilated ophthalmoscopy including vitreous, macula, retina periphery, lens status and opacification and optic nerve will be performed at Screening, Baseline and Month 12/Exit visits. No severity grade will be assigned for vitreous, retina periphery and macula findings, and summarized together with biomicroscopy findings as non-gradable findings.

5.4.6.6.1. Optic Disc Examination

Optic Nerve cup/disc ratio will be evaluated using a 0.0 to 1.0 scale, with larger values indicating glaucoma or other pathologies, thus a reduction from baseline is considered an improvement. Categorical changes in cup/disc ratio from baseline will be summarized for post-Baseline visit. Change from baseline at the follow-up visit (visit value -baseline values) will be categorized as an improvement of 0.2 or more (≤ -0.2), no change -between 0.2 and -0.2 (> -0.2 to < 0.2), or a worsening if the ratio increases by 0.2 or more (ie, change ≥ 0.2). The number and percentage of participants in each category will be provided for treatment cohorts.

5.4.6.6.2. Lens Status and Opacification

At follow-up visits, the lens opacity will be assessed only for eyes evaluated as phakic at baseline. The presence and severity of nuclear, cortical, and posterior subcapsular cataract lens

opacities using a 3-point scale (< standard photo #2, and \geq standard photo #2) will be summarized by treatment cohorts and by visit.

5.4.6.7. Gonioscopy and Bimatoprost SR Implant Assessment

Gonioscopy will be performed to assess the inferior iridocorneal (anterior chamber) angle. Participants presenting with peripheral anterior synechiae on gonioscopy at any time during the study will be presented in a listing with the time in which it occurred.

Number and percentage of participants with an implant visible during the study will be summarized in a tabular format further breaking down by the categorical percentage visible of the implant. Also, the number and percentage of participants who have an implant in contact with corneal endothelium at any visit will be summarized. Implant assessment will be presented as data listings displaying the location of implant (12 zones) and status of contact with corneal endothelium for each participant.

5.5. Interim Analyses

There are no planned interim analyses. Safety analyses may be periodically performed based on relevant data snapshots.

There will be two database locks as described in Section 5.1. Analyses will be performed after each lock. The primary and secondary efficacy analysis based on the first database lock will be considered as the final analysis. The analyses based on the second database lock provide further efficacy and safety information.

5.5.1. Data Monitoring Committee

A data monitoring committee is not required for this study.

6. Supporting Documentation

Additional baseline characteristics, and pre-defined safety criteria can be found in Section 6.2 Appendix 2.

6.1. Appendix 1: List of Abbreviations

Abbreviation	Definition
AE	Adverse event
ALT	Alanine aminotransferase
AST	Aspartate aminotransferase
ATC	Anatomical Therapeutic Chemical
BCVA	Best corrected visual acuity
BMI	Body mass index
BUN	blood urea nitrogen
CCT	central corneal thickness
CECD	Central endothelial cell density
CI	Confidence interval
CV	Coefficient of variation
eCRF	Electronic case report form
FAS	Full analysis set
HEX	Pleomorphism
IOP	Intraocular pressure
IWRS	Interactive web response system
KM	Kaplan-Meier
MCHC	Mean corpuscular hemoglobin concentration
MCH	Mean corpuscular hemoglobin
MCV	Mean corpuscular volume
MD	Mean defect
MedDRA	Medical Dictionary for Regulatory Activities
NA	Not applicable
OAG	Open-angle glaucoma
OHT	Ocular hypertension
OU	Both eyes
PT	Preferred term
RBC	Red blood cell
SAE	Serious adverse event
SAP	Statistical analysis plan
SAF	Safety analysis set
SAS	Statistical Analysis Software

Abbreviation	Definition
SD	Standard deviation
SE	Study eye
SoA	Schedule of activities
SOC	System organ class
SR	Sustained release
SUN	Standardization of the Uveitis Nomenclature
TEAE	Treatment-emergent adverse event
TESAE	Treatment-emergent serious adverse event
USA	United States
VA	Visual Acuity
WBC	White blood cell
WHO	World Health Organization
WOCBP	Woman of childbearing potential

6.2. Appendix 2: Supporting Study Information

6.2.1. Demographics

Demographic parameters (age, sex, race, ethnicity) will be summarized descriptively by treatment cohort for the FAS population.

6.2.2. Baseline and Disease Characteristics

Baseline characteristics will be summarized descriptively (height, weight, BMI) by treatment cohort for the FAS population including general and ocular inclusion criteria. The following ocular baseline and disease characteristics will be presented for the study eye in both treatment cohorts: diagnosis (of OAG or OHT), Baseline Hour 0 IOP, iridocorneal angle Shaffer grade, Baseline central endothelial cell density, and Baseline lens status.

6.2.3. Protocol Deviations

Unique participants reporting significant protocol deviations will be summarized in total and by treatment cohort for the FAS population. A listing of any significant protocol deviations will be provided.

6.2.4. Medical History

Abnormalities in participants' medical and surgical history data will be coded using the MedDRA dictionary. Ophthalmic and non-ophthalmic medical and surgical history will be summarized by treatment cohort for the SAF population.

6.2.5. Prior/Concomitant Medications

The medication data will be coded using the most recent version of World Health Organization (WHO) Drug Dictionary Enhanced.

Prior medication is defined as any medication taken prior to the start of study intervention regardless of stop date of the medication. Concomitant medication is defined as any medication taken after the start of study intervention regardless of the start date of the medication.

Prior and concomitant medications will be coded using the Anatomical Therapeutic Chemical code (4th level, or most specific level available if 4th level is unavailable).

The number and percentage of participants reporting prior or concomitant medications will be summarized by treatment cohort, ATC class and code, and preferred drug name. If more than one medication is coded to the same preferred drug name for the same participant, the participant will be counted only once for that preferred drug name. Prior and concomitant medications will be summarized separately.

6.3. Appendix 3: Data Handling Convention

6.3.1. Visit Timepoints

Table 6-1 and **Table 6-2** present the analysis visits assigned for efficacy and safety assessments for participants for both the Bimatoprost SR and LUMIGAN 0.01% cohorts. Depending on safety assessments schedule, either **Table 6-1** or **Table 6-2** will be used for by visit analysis. If the assessment date is on or after the date of the administration of Bimatoprost SR (or date of the first self-administration of LUMIGAN 0.01%), the study day is calculated by assessment date – date of the first administration or dose of study treatment + 1. If the assessment date is before the date of the first administration or dose of study treatment, the study day is calculated by assessment date – date of the first administration or dose of study treatment. Therefore, a negative day indicates a day before the start of the study treatment.

Table 6-1 Efficacy and Safety Visit Window

Visit Name	Target Day of the visit ^a	Analysis Visit Window
Baseline Office	-7 to -1 from Baseline Sleep Lab visit	≤ Baseline Sleep Lab-1
Baseline Sleep Lab	0 ^b	≤ Administration Day 1-1
Administration Day 1	1	1
Day 2 Safety	2	2
Week 8 Office	-7 to -1 from Week 8 Sleep Lab visit	≤ Week 8 Sleep Lab visit - 1
Week 8 Sleep Lab	56 ^c	[42, 70]
Week 16	112	[71, 142]
Month 6	180	[143, 225]
Month 9	270	[226, 315]
Month 12/Study Exit	360	≥ 316

^a Relative to the date of treatment administration.

^b Must be different than Baseline Office visit.

^c Different than Week 8 Office visit.

Table 6-2 Safety Visit Windows

Visit Name	Target Day of the visit ^a	Analysis Visit Window
Baseline Office	-7 to -1 from Baseline Sleep Lab visit	≤ Baseline Sleep Lab-1
Administration Day 1	1	1
Week 16	112	[2, 142]
Month 6	180	[143, 225]
Month 9	270	[226, 315]
Month 12/Study Exit	360	≥ 316

^a Relative to the date of treatment administration.

If multiple assessments (scheduled or unscheduled visits) were taken within an analysis window, the assessment obtained on the day closest to the target day will be used; in the case of a tie, the assessment obtained on the later day will be used in the analysis. For participants treated with Lumigan, the exit visit assessments will be summarized in Month 12/study exit regardless of the last visit falls into. Be noted, IOP values will be also measured for safety, and these safety IOP values recorded on unscheduled IOP eCRF page. Unscheduled IOP values in an analysis windows will not be used for efficacy analysis, unless the IOP value is the only one in the analysis visit window. For 24 hour time-match IOP analysis, IOP assessments at Week 8 sleep lab visit will be used and unscheduled visit assessments will not be used.

Table 6-3 presents the time window for IOP measurements during the Office and Sleep Lab visits at Baseline and Week 8 for both the Bimatoprost SR and LUMIGAN 0.01% cohorts. During each assessment, two consecutive IOP measurements will be taken of study eye. If the first 2 measurements differ by > 1 mm Hg, a third measurement will be taken. If the first 2 measurements differ by ≤ 1 mm Hg, the IOP for the given eye will be the average of the 2 readings. If the difference between the first 2 measurements is > 1 mm Hg, the IOP for the given eye will be the median of the 3 readings.

Table 6-3 IOP Measurement Time Windows

Visit Name	Assessment Name	Assessment Type	Target Time of the Assessment	Analysis Time Window
Sleep Lab ^a	24-hour IOP Measurements	Diurnal	08:00	07:15 to 08:45
			10:00	09:15 to 10:45
			12:00	11:15 to 12:45
			14:00	13:15 to 14:45
			16:00	15:15 to 16:45
			18:00	17:15 to 18:45
			20:00	19:15 to 20:45
			22:00	21:15 to 22:45
		Nocturnal	00:00	23:15 to 00:45
			02:00	01:15 to 02:45
			04:00	03:15 to 04:45
			06:00	05:15 to 06:45
Office ^b	Hour 0 IOP Measurement	N/A	08:00	06:30 to 09:30

a For both Baseline and Week 8

b For Baseline office visit, Day 2 safety visit, Week 8 office visit, Week 16, Month 6, 9, and 12/Exit

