5.3.1. Analysis Endpoint(s)

- The primary efficacy endpoint is the time-matched IOP change from baseline at the Week 8 Sleep Lab visit from the 24-hour IOP data collected at the Baseline Sleep Lab visit in the study eye for the Bimatoprost SR cohort.
- The secondary efficacy endpoint is the change from baseline in range of IOP in eyes treated with Bimatoprost SR at Week 8 Sleep Lab visit.
- Other efficacy endpoints include:
 - Time-matched IOP change from baseline in a supine position.
 - Hour 0 IOP change from baseline through Month 12.
 - Time to initial use of nonstudy IOP-lowering treatment.

Refer to Section 6.3 Appendix 3 for details on IOP measurement conventions and corresponding time windows.

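### The Week 8 Office window in SAP Table 6-1 has no lower bound and depends on the Sleep Lab date, so the Week 8 Hour 0 summary can take an off-target reading or lose a valid one

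*SAP*

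**What the plan says.** All the rules are in SAP section 6.3.1.

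- **Window.** Table 6-1 gives the Week 8 Office row the window "≤ Week 8 Sleep Lab visit - 1". Its target is also relative to the other visit: minus "7 to -1 from Week 8 Sleep Lab visit". The Week 8 Sleep Lab row has its own window, Days 42 to 70, with target Day 56. Day 2 has a separate row with window 2.
- **Choice within a window.** When several assessments fall in one window, "the assessment obtained on the day closest to the target day will be used", and the later day wins a tie. No maximum distance from the target is set.
- **Unscheduled readings.** IOP is also measured for safety, with "these safety IOP values recorded on unscheduled IOP eCRF page". Such values stay out of efficacy "unless the IOP value is the only one in the analysis visit window".
- **24-hour analysis.** Here "IOP assessments at Week 8 sleep lab visit will be used and unscheduled visit assessments will not be used".
- **Clock time.** Table 6-3 limits Hour 0 readings to 06:30 to 09:30. Its footnote applies this "For Baseline office visit, Day 2 safety visit, Week 8 office visit, Week 16, Month 6, 9, and 12/Exit".

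The endpoint concerned, "Hour 0 IOP change from baseline through Month 12", is listed among the other efficacy endpoints in SAP 5.3.1. SAP 5.3.4.3 summarises it by visit and graphs it for the study eye in the Bimatoprost SR cohort.

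**The concern.** A by-visit mean should come from readings taken near that visit. Every other post-treatment row of Table 6-1 has a lower limit or is a single day; the Week 8 Office row has neither. Any post-treatment day before the Sleep Lab visit qualifies, and section 6.3.1 does not say that an assessment may fill only one row. The row also has no meaning when the Sleep Lab date does not exist, and no fallback is given.

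At stake is the Week 8 point on the Hour 0 curve. It could include a value from the day after the procedure, or a safety reading from weeks earlier, shown as Week 8. It could also omit a correctly timed Goldmann reading because the participant did not attend the overnight visit.

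**Working it through.** The plan states no figure to reproduce, so the check applies the table's rules to study days and to example participants.

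**Inputs.** Table 6-1 windows and the selection rules of SAP 6.3.1. From the schedule of activities: Sleep Lab within 7 days of Week 8 (Day 56), and Office visit up to 7 days before it, on a different day. Only post-treatment days are counted, although the open bound read literally admits earlier ones too.

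**How much of the window is off target.** With the Sleep Lab on Day S, the window holds Days 1 to S − 1, which is S − 1 days. The target range, Days S − 7 to S − 1, holds 7. Days outside it = (S − 1) − 7.

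| Sleep Lab day S | Days in window | Outside target | Share |
|---|---|---|---|
| 49 | 48 | 41 | 41/48 = 85% |
| 56 | 55 | 48 | 48/55 = 87% |
| 63 | 62 | 55 | 55/62 = 89% |

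Days 3 to 41 (39 days) belong to the Week 8 Office row and to no other row of Table 6-1.

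**Which value is reported as Week 8 Hour 0.** Reading A lets one assessment fall in two rows. Reading B assigns each assessment to one row.

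| Participant | Reading A | Reading B |
|---|---|---|
| 1. Day 2 and Office Day 50; Sleep Lab Day 56 | Day 50 | Day 50 |
| 2. Day 2 only; Office reading missing; Sleep Lab Day 56 | Day 2 | missing |
| 3. Day 2 and one unscheduled on Day 20; Office missing; Sleep Lab Day 56 | Day 2 | Day 20 |
| 4. One unscheduled on Day 20; Day 2 and Office missing; Sleep Lab Day 56 | Day 20 | Day 20 |
| 5. Day 2 and Office Day 50; Sleep Lab missed | no window | no window |
| 6. Day 2 and Office Day 58, after Sleep Lab Day 56 | Day 2 | missing |

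In row 2 under A, the value used lies 49 − 2 = 47 days before the nearest target day. In row 5 the Day 50 reading falls by day only in the Sleep Lab row. That row is for the 24-hour measurements, which Protocol 8.1 takes with a different tonometer from the Goldmann instrument used at Hour 0.

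**Effect on the mean.** One wrong value that differs by d mm Hg moves a mean of n readings by d/n. If d is assumed to be 4 to 6 mm Hg and n is 20 (the planned minimum of evaluable participants), the shift is 4/20 = 0.2 to 6/20 = 0.3 mm Hg per affected participant. The documents give no value for d and no count of affected participants.

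**The case against.** The strongest reply is that the Day 2 problem needs a strained reading. The tables assign analysis visits to assessments and Day 2 has its own row, so one row per assessment is the natural understanding; a programmer would also probably fall back on the recorded visit name when the Sleep Lab date is absent. The first part stands in so far as a Day 2 substitution is possible, not certain. It does not clear the rule: under that same reading, row 3 of the table reports an unscheduled Day 20 value as Week 8, and row 5 still has no window. A sensible fallback is not a prespecified one.

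A reader might infer more than the documents support:

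- **Both substitutions at once.** They are alternatives. If Day 2 counts in the window, an unscheduled value is no longer alone there and is barred.
- **Up to 33% of participants exposed.** The 33% in SAP section 3 allows for premature discontinuation. Someone who leaves before Week 8 has no Sleep Lab date, so nothing is substituted. Substitution needs a Sleep Lab visit without an in-window Office reading, and no rate is given for that.
- **Unscheduled readings escape the clock limit.** A reading assigned to the Week 8 Office row comes under that visit's 06:30 to 09:30 limit in Table 6-3.
- **All unscheduled readings should be dropped.** Post-rescue values are already excluded (SAP 4.2). Protocol 6.5.3 foresees unscheduled visits to confirm inadequate IOP control, so a pre-rescue reading that is a participant's only value may come from a poorly controlled eye. Removing it could flatter the mean.
- **The main results are at risk.** The 24-hour analysis uses Sleep Lab readings only.

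**Conclusion.** The Week 8 Office window is wrong as written. It can label an off-target reading as Week 8 when the Sleep Lab is attended without a usable Office Hour 0 reading, and it leaves a valid Office reading without a window when the Sleep Lab visit is missed. Both faults follow from the table's text; which off-target reading enters depends on whether windows may overlap, and the SAP does not say.

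The consequence is minor. It is confined to one descriptive endpoint in a study with no hypotheses, and the closest-to-target rule picks the scheduled reading whenever it is present and in window. The size cannot be computed from the documents; 0.2 to 0.3 mm Hg per affected participant is only an illustration resting on an assumed difference of 4 to 6 mm Hg and 20 readings. The point is worth correcting because the correction is almost free.

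**What to change.** Replace the cell with a fixed study-day window that does not refer to the Sleep Lab date and covers every Office visit paired with an accepted Sleep Lab visit. The SAP accepts the Sleep Lab on Days 42 to 70, and an Office visit 1 to 7 days earlier falls on Days 42 − 7 = 35 to 70 − 1 = 69. Days 35 to 70 therefore suffice, and stop short of the Week 16 window at Day 71. A window starting at Day 42 would leave out Office visits on Days 35 to 41.

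Give it a single target day, for example Day 52. Protocol-compliant Office visits fall on Days 49 − 7 = 42 to 63 − 1 = 62, with midpoint (42 + 62)/2 = 52.

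State that each assessment is assigned to one analysis visit only. Because the two Week 8 rows would share Days 42 to 70, add that the Office row takes Hour 0 readings and the Sleep Lab row takes 24-hour readings. Keep the last-resort rule for unscheduled values inside the bounded window, and keep the 06:30 to 09:30 limit.

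In the examples above, rows 5 and 6 would then use the Office reading and rows 2 to 4 would be missing. The cost is one table row and a sentence or two in the SAP, and a few participants with a missing Week 8 Hour 0 value in place of an off-target one.

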a Eligibility criteria may be rechecked at any time prior to and during washout, at the discretion of the investigator.

b Washout in both eyes may begin after all screening procedures have been completed.

c Office visit procedures may be performed up to 7 days prior to Sleep Lab visit.

d Perform 24-hour Sleep Lab visit on a different day from all other Office visit study procedures.

e At sites where required by local institution or health authority, a serum test may be done, with negative results for all tests confirmed prior to the time of Bimatoprost SR administration. Pregnancy testing at Baseline is required regardless.

f Blood and urine samples are collected only at Screening unless a retest is necessary.

g Manifest refraction will be used to provide a correction for best-corrected visual acuity testing. At all study visits, if there is a 2-line or more reduction in visual acuity from the last best-corrected visual acuity performed, a repeat manifest refraction in both eyes and best-corrected visual acuity will be performed.

h At selected sites/selected participants only, anterior segment imaging may be performed in both eyes of consenting participants using Allergan-approved instruments.

i For a given participant, the same test methodology must be used for all visual fields performed at Screening, Baseline, and throughout the study.

j For a given participant, the same specular microscope model and analysis methodology must be used at Screening, Baseline, and throughout the study.

k Screening: participant number; Baseline: Hour 0 IOP; Day 1: enrollment after eligibility confirmation (may be done at end of Baseline visit if needed)

l All 24-hour Sleep Lab visit IOP exams will be performed with an Allergan-specified tonometer. Diurnal IOP measurements will be taken supine ≥ 5 minutes at rest then sitting ≥ 5 minutes at rest at 8:00 ± 30 min, 10:00 ± 30 min, 12:00 ± 30 min, 14:00 ± 30 min, 16:00 ± 30 min, 18:00 ± 30 min, 20:00 ± 30 min, and 22:00 ± 30 min. Nocturnal IOP measurements will be taken supine only ≥ 5 minutes at rest 00:00 ± 30 min, 02:00 ± 30 min, 04:00 ± 30 min, and 06:00 ± 30 min. Please see Procedure Manual for details.

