#### **4.4. End of Study Definition**

The end of the study is defined as the date of the last visit of the last participant in the study or last scheduled procedure shown in the SoA for the last participant in the study.

A participant assigned and treated with Bimatoprost SR is considered to have completed the study if he/she has completed all visits of the study to Month 12. At the Month 12/Study Exit visit, if the investigator determines that any safety concerns warrant participant follow-up, the participant may be followed post exit until safety concerns are resolved based on the investigator's discretion. Participants assigned and treated with LUMIGAN 0.01% may early exit the study after completion of the Week 8 Sleep Lab visit, if there are no safety concerns in the opinion of the investigator, and at which time all assessments performed at the Month 12/Study Exit visit should be performed.

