### 7.2. Participant Discontinuation/Withdrawal from the Study

- A participant may withdraw from the study at any time at his/her own request, or may be withdrawn at any time at the discretion of the investigator for safety, behavioral, compliance, or administrative reasons.
- If a participant develops (or has an exacerbation of) a medical condition that, in the opinion of the investigator, would put the participant at an unacceptable medical risk by continuing study participation, the participant will be withdrawn from the study.
- If the participant withdraws consent for disclosure of future information, the sponsor may retain and continue to use any data collected before such a withdrawal of consent.
- If a participant withdraws from the study, he/she may request destruction of any samples taken and not tested, and the investigator must document this in the site study records.

- Participants assigned to and treated with Bimatoprost SR who have received nonstudy IOP-lowering treatment (rescue) in the study eye, will be followed for the duration of the study through the Month 12/Exit visit. If the implant has been removed, the participant may discontinue the study if based on investigator assessment the eye is in stable condition, at which time they should complete the Month 12/Exit visit procedures. Notification of early participant discontinuation from the study and the reason for discontinuation will be made to Allergan and will be clearly documented on the appropriate case report form. If participants discontinue before Month 12/Exit, the site should complete all procedures for the Month 12/Exit visit at the participant's last visit.

The investigator should consider withdrawing a participant from the study early if any of the following criteria are met:

- Participant develops (or has an exacerbation of) a medical condition that, in the opinion of the investigator, compromises the participant's ability to participate in the study
- Participant is unwilling or unable to continue to comply with study procedures
- Participant is unwilling or unable to continue in the study

Whenever possible, the decision to withdraw a participant from the study or study treatment should be discussed with Allergan.

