1.2.4. End of Study Definition

The end of the study is defined as the date of the last visit of the last participant in the study or last scheduled procedure shown in the SoA for the last participant in the study.

A participant assigned and treated with Bimatoprost SR is considered to have completed the study if he/she has completed all visits of the study to Month 12. At the Month 12/Study Exit visit, if the investigator determines that any safety concerns warrant participant follow-up, the participant may be followed post exit until safety concerns are resolved based on the investigator's discretion. Participants assigned and treated with LUMIGAN 0.01% may early

exit the study after completion of the Week 8 Sleep Lab visit, if there are no safety concerns in the opinion of the investigator. For the LUMIGAN cohort, an exit visit will be performed after the Week 8 Sleep Lab visit where all assessments scheduled for the Month 12/Study Exit visit will be performed.

2. Statistical Hypotheses

There are no statistical hypotheses for this study.

3. Sample Size Determination

The sample size is based on practical considerations. Approximately 35 participants will be enrolled: 25 to 30 in the Bimatoprost SR cohort and 5 in the LUMIGAN 0.01% cohort.

Twenty-five to 30 participants will be enrolled in the Bimatoprost SR cohort to achieve a minimum total of 20 evaluable participants, defined as participants with sufficient data at baseline and Week 8 to evaluate the 24-hour IOP-lowering effect of Bimatoprost SR. This assumes a premature discontinuation rate of up to 33%. Participants who prematurely discontinue from the study will not be replaced. Participants will be assigned to the Bimatoprost SR or LUMIGAN 0.01% cohort [REDACTED].

4. Populations for Analysis

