5.3.4.3. Hour 0 IOP Analyses

The descriptive summary for Hour 0 IOP values in a sitting position at baseline with corresponding change from baseline by visit through Month 12/Study Exit will be performed by treatment cohorts for the study eye in Bimatoprost SR and Lumigan 0.01% cohorts and pooled treatment cohorts for the fellow eye. The mean of the Hour 0 IOP and the Hour 0 IOP change from baseline for each visit will be presented graphically for the study eye in the Bimatoprost SR cohort.

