5.4. Safety Analysis

Descriptive statistics will be used to summarize the safety data by cohorts based on the SAF. The safety parameters will include the following non-ocular safety parameters: non-ocular AEs and vital signs; ocular safety parameters: visual field examination, visual acuity, macroscopic conjunctival hyperemia assessment, biomicroscopy, dilated ophthalmoscopy (including optic disc assessment), pachymetry, gonioscopy (including angle assessment), and specular microscopy. Results from ocular safety assessments will be summarized by participants and listed, including scheduled and unscheduled assessments (if any). The results will be presented by treatment cohorts for the study eye and pooled treatment cohorts for the fellow eye. Unless

otherwise stated, the last nonmissing safety assessment before the first dose of study treatment will be used as the baseline for all analyses of that safety parameter.

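### SAP 6.3.1 files LUMIGAN exit data under Month 12/Study Exit on any study day, so values from about two months can enter the pooled fellow-eye Month 12 row

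*SAP*

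**What the plan says.** SAP 6.3.1 introduces Tables 6-1 and 6-2, which "present the analysis visits assigned for efficacy and safety assessments for participants for both the Bimatoprost SR and LUMIGAN 0.01% cohorts". Both tables give Month 12/Study Exit a target of Day 360 and admit assessments from Day 316 onward. The text after the tables then sets this bound aside for one cohort: "For participants treated with Lumigan, the exit visit assessments will be summarized in Month 12/study exit regardless of the last visit falls into".

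Under Protocol 4.4, LUMIGAN participants "may early exit the study after completion of the Week 8 Sleep Lab visit" if the investigator has no safety concern, and the Month 12/Study Exit assessments are done at that time. SAP 1.2.4 adds: "For the LUMIGAN cohort, an exit visit will be performed after the Week 8 Sleep Lab visit". Bimatoprost SR participants who leave early have the same assessments (Protocol 7.2: "If participants discontinue before Month 12/Exit, the site should complete all procedures for the Month 12/Exit visit"), but the SAP gives them no exception to the day windows.

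SAP 5.3.4.3 summarizes Hour 0 IOP by visit through Month 12/Study Exit "for the study eye in Bimatoprost SR and Lumigan 0.01% cohorts and pooled treatment cohorts for the fellow eye". SAP 5.4 sets a general rule for ocular safety: "The results will be presented by treatment cohorts for the study eye and pooled treatment cohorts for the fellow eye". The subsections on endothelial cell density, pachymetry, optic disc and lens (5.4.6.4, 5.4.6.5, 5.4.6.6.1, 5.4.6.6.2) refer only to treatment cohorts, and the visual field subsection (5.4.6.2) refers to eye and visit.

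**The concern.** The exception gives one row label two meanings. For SR participants it means an assessment on Day 316 or later. For LUMIGAN participants it means the last visit, whenever that was. In the LUMIGAN study-eye row this is a labelling problem: a reader may take two-month values for one-year values. In the pooled fellow-eye row the two kinds of value go into one summary, and the reader cannot separate them.

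Fellow eyes receive standard of care, which under Protocol 6.5.2 can include medication, laser or surgery during follow-up. Values at two and twelve months therefore cannot be assumed interchangeable. At stake is the reading of some descriptive by-visit tables. No hypothesis test is involved.

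**Working it through.** **Inputs**
- Planned enrolment: 25 to 30 SR and 5 LUMIGAN (SAP 3). 30 + 5 = 35 reproduces the plan's total of approximately 35, and the lower end is 25 + 5 = 30.
- Week 8 Sleep Lab visit: target Day 56 (SAP Table 6-1), visit window ± 7 days (Protocol Table 1-1), so Day 49 to Day 63.
- Month 12/Study Exit: Day 316 or later, target Day 360 (SAP Tables 6-1 and 6-2).
- The Sleep Lab visit runs from 08:00 to a last reading at 06:00 the next morning (Protocol 8.1).
- Office procedures are kept apart from it: "Perform 24-hour Sleep Lab visit on a different day from all other Office visit study procedures".

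**Earliest exit**
- A Sleep Lab visit starting on Day 56 ends on Day 57, so the earliest exit is about Day 57. It is a day later if the visit is counted as occupying both dates.
- Distance to the row's lower bound: 316 − 57 = 259 days.
- Distance to target: 360 − 57 = 303 days, or 303/30 = 10.1 of the SAP's 30-day months (360/12 = 30).
- For Sleep Lab visits starting on Day 49 to 63, the earliest exit is about Day 50 to 64. That is 316 − 64 = 252 to 316 − 50 = 266 days before the bound, and 360 − 64 = 296 to 360 − 50 = 310 days before target.
- No latest exit day is set. Any LUMIGAN exit up to Day 315 is filed differently from an SR exit on the same day. From Day 316 the two rules agree.

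**Same day, two cohorts**

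| Exit day | SR | LUMIGAN |
|---|---|---|
| 57, assessments on Table 6-2 | Week 16 [2, 142] | Month 12/Study Exit |
| 180, either table | Month 6 [143, 225] | Month 12/Study Exit |
| 316 or later | Month 12/Study Exit | Month 12/Study Exit |

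**Share of the pooled fellow-eye row**, w = early LUMIGAN exits / all participants in the row
- All 5 exit early, no SR loss: 5/(5 + 30) = 14.3%; 5/(5 + 25) = 16.7%.
- All 5 exit early, 20 SR left: 5/25 = 20%. This is illustrative. The documents' figure of 20 is the Week 8 evaluable minimum, and they give no Month 12 attrition figure.
- 1 exits early and the other 4 reach Month 12, no SR loss: 1/35 = 2.9%; 1/30 = 3.3%.

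**Effect on a pooled mean**, shift from the SR mean = w × D, where D is the early-LUMIGAN minus SR difference in fellow-eye means. The documents give no value for D. Assuming 1 to 3 mm Hg in size:
- 30 SR: 0.14 to 0.43 mm Hg.
- 25 SR: 0.17 to 0.50 mm Hg.

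The sign of D is unknown.

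**The case against.** The strongest reply is that this is an open convention. The SAP says where the LUMIGAN exit data go, the row label includes Study Exit, the study is descriptive, the fellow eye carries no primary or secondary endpoint, and SAP 6.3.2 puts every assessment in the listings. The exception also has a purpose. An Hour 0 IOP taken after the Week 8 Sleep Lab visit has no natural Week 8 row: Table 6-3 ties Hour 0 to the office visit, and the Week 8 Office window closes the day before the Sleep Lab visit. For optic disc and lens, Month 12/Exit is the only scheduled post-baseline visit.

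Much of this stands, and it keeps the point minor. Giving these data a place is reasonable, and disclosure largely answers the concern for the LUMIGAN study-eye row. It does not answer it for the pooled row. The words Study Exit do not describe that row, because SR exits before Day 316 are not in it. Listings do not change a summary already computed. The last-assessment rule in SAP 6.3.2 concerns repeated or unscheduled safety assessments, so it does not remove early LUMIGAN values.

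A reader might infer that values are averaged across cohorts in all six by-visit summaries: Hour 0 IOP, visual field, endothelial cell density, corneal thickness, cup/disc ratio and lens opacity. The documents do not support that. Pooling is explicit only for Hour 0 IOP. For the other five it rests on the general sentence in SAP 5.4, while four of their subsections refer only to treatment cohorts. Cup/disc categories, lens opacity and visual field findings are counts, so early and late observations would be mixed there but not averaged.

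A reader might also take the Sleep Lab analysis window [42, 70] to allow an exit on Day 43. That requires a Sleep Lab visit outside the ± 7-day visit window.

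**Conclusion.** The point holds and is minor. Followed as written, the SAP lets LUMIGAN values from about two months enter a pooled fellow-eye Month 12/Study Exit row from which SR exits before Day 316 are excluded. No other passage corrects this. It is secure for Hour 0 IOP. For the ocular safety tables it depends on the general pooling rule being applied.

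At most 5 participants are affected, and possibly none, because early exit is optional. The 14.3% to 16.7% share assumes that all 5 exit early, that no SR participant is lost and that everyone contributes a fellow-eye value. SR loss raises it, and denominators will differ by table. The 10-month gap assumes an exit soon after an on-schedule Sleep Lab visit and SR values near target.

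It would be wrong to infer that the efficacy conclusions or an SR-versus-LUMIGAN comparison are biased. The primary and secondary analyses use Week 8 Sleep Lab data, SR study-eye rows contain no LUMIGAN values, and nothing in the documents fixes the sign of any shift.

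**What to change.** Replace the sentence in SAP 6.3.1 with a rule to this effect:

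> LUMIGAN exit assessments before Day 316 are shown in a separate row, LUMIGAN early exit, with n and the median and range of study day. They are excluded from the pooled fellow-eye Month 12/Study Exit row. They stay in last-visit, worst-value and any-visit summaries and in the listings. LUMIGAN exit assessments on or after Day 316 stay in Month 12/Study Exit.

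For the LUMIGAN study-eye row, a footnote with n and study day would be enough. It would not be enough for the pooled fellow-eye row, where the values are combined.

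The cost is one SAP rule and one added row in up to six summaries. No data are dropped and none are newly collected. The LUMIGAN Month 12 cell may be nearly empty. Some asymmetry remains, since an early SR exit still goes to its day window while an early LUMIGAN exit goes to its own row, but the label and study day would make that visible.
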